5.8 Study Drug Compliance

Dosing will be done by the subject or subject's caregiver at home throughout the study. Prior to discharge from each scheduled site visit, subjects will be given sufficient study drug for at-home dosing until the next scheduled visit.

Subjects will be instructed to return all unused study drug including the kits at each clinic visit, in order to allow the assessment of compliance with the study treatment. See [Section 5.3](#) for details on how study drug will be packaged. Subjects will be instructed to return all used and unused devices unless otherwise indicated per local policy.

Compliance will be determined based on the amount of unused drug returned. Acceptable compliance for the study is defined as $\geq 80\%$ of planned study drug administration.

Consequences of noncompliance will lead to retraining and/or discontinuation of study drug as described in [Section 6.8](#). In case of overdose see [Section 7.9](#).

5.9 Prior and Concomitant Therapy

Record in the eCRF all prior (therapy taken within 30 days of the Screening/Baseline Visit) and concomitant therapies (e.g., medicines or nondrug interactions) used from the time the subject signs the informed consent until completion of the study, including any changes. For prescription and over-the-counter medicines, vaccines, vitamins, and herbal supplements, record the name, reason for use, dates administered, and dosing information (according to the eCRF completion guidelines).

Record in the eCRF information regarding vaccination against SARS-CoV-2 (including any booster vaccination), for any subject that has received the vaccine at any time prior to Screening. See [Section 6.7](#) regarding considerations for SARS-CoV-2 and variants. Contact the CRO Medical Monitor for any questions on concomitant or prior therapy.

5.9.1 Permitted Medicines

Any medications that are considered necessary to protect subject welfare and will not interfere with the study medication may be given at the Investigator's discretion.

Permitted medications are any medications that are required by the subject during the course of the study, and which are not specifically prohibited by the protocol. Any such medications prescribed or used must be recorded in the eCRF.

Any additional concomitant therapy that becomes necessary during the study and any change to concomitant drugs must be recorded in the corresponding section of the eCRF, noting the name, dose, duration, and indication of each drug (according to the eCRF completion guidelines). Of note, any newly prescribed or changes to diuretic therapy (dose, frequency, etc.) should be captured in the eCRF.

5.9.1.1 Permitted PAH Medicines

The addition of a new PAH therapy(ies) must be documented in the eCRF as well as in the concomitant therapy section. At this time there is no drug interaction data with AV-101 and inhaled prostacyclins and so any inhaled prostacyclin should not be used while taking AV-101 in the LTE study.

5.9.2 Prohibited Medicines

The following treatments are not permitted during the study:

- Inhaled prostacyclin therapies
- Warfarin (or any vitamin K antagonists), DOACs or dual antiplatelet therapy

Use of any of the above nonpermitted medicines and therapies require IMP discontinuation (see [Section 6.8](#)) (anti-platelet monotherapy with e.g. aspirin or clopidogrel is allowed).

The use of strong CYP3A4 inhibitors may increase the systemic exposure to imatinib. Likewise, strong CYP3A4 inducers may decrease the exposure of imatinib. It is unknown what contribution of systemically circulating AV-101 will contribute to potential efficacy or adverse events and so alternatives to strong CYP3A4 inhibitors or inducers should be considered.

High doses of oral imatinib are known to have the potential to prolong the QTc interval on the ECG. Drugs that are known to increase the QT interval should be used with caution. For a list of such drugs please refer to <https://crediblemeds.org>. In the event that a subject develops an absolute prolongation of the QTc interval to a value > 500 msec, or develops a change from baseline in the QTc interval of ≥ 60 msec, the subject should undergo a dose reduction. If a subject has already undergone a dose reduction for other reasons, then they should discontinue study drug. The subject should return for an unscheduled visit after two weeks of dose reduction and the ECG should be repeated. If there is a shortening of the QTc interval to < 500 msec, or the change from baseline is

now < 60 msec, the subject should remain on the reduced dose. If there is no change in the QTc interval after reducing the dose then the subject should be discontinued from study drug.

6 Study Assessments and Procedures

Before subjects commence any study-specific activities or procedures, including Week 24 assessments from AV-101-002 which will serve as baseline for this study, the Sponsor requires a copy of the study site's written Independent Ethics Committee/Institutional Review Board (IEC/IRB) approval of the protocol, informed consent form (ICF), and all other subject information and/or recruitment material, if applicable. Each subject must sign and date the ICF before participating in study-specific activities. If an unexpected circumstance occurs that would prohibit the subject from entering the study at Week 24 on AV-101-002, this may be discussed with the CRO Medical Monitor and/or Sponsor.

The Week 24 end of study visit of the parent study (AV-101-002) also represents the baseline visit for the LTE study (AV-101-003). The following assessments will be conducted/collected during the baseline visit of the LTE and at selected time points specified in the Schedule of Assessments (Table 1). Additional procedures deemed necessary as part of standard of care may be performed at the discretion of the Investigator. All missed visits and any performed procedures that are not protocol-specified activities must be documented in the subject's medical record and the appropriate eCRF. General considerations for study visits include, but are not limited to the following:

- No protocol waivers or exemptions are allowed.
- Immediate safety concerns should be discussed with the CRO Medical Monitor immediately upon occurrence or awareness to determine if the subject should continue or discontinue study drug.
- Adherence to the study design requirements, including those specified in the Schedule of Assessments, is essential and required for study conduct (see Section 6.7.1 for COVID-19 considerations).
- The Investigator will obtain written informed consent before the end of study visit for study AV-101-002 and as specified in Section 9.1.3 (Informed Consent Process). Upon the subject's agreement, their primary health care provider should be informed about the subject's enrollment in the study.
- Order of Procedures:
 - Health-related QoL assessments should be performed prior to all other study procedures.
 - Vital signs should be collected prior to blood draws. Blood samples for NT-proBNP levels should be collected prior to the 6MWT.
 - All other study assessments should also be performed, according to the Schedule of Assessments (Table 1).
- **Unscheduled visits:** may occur at any time during the study with the assessments to be performed according to the Investigator's judgment. Unscheduled visits may also be necessary for study drug dispensing following temporary withdrawal as described in Sections 6.7 and 7.7.

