The systemic safety of imatinib mesylate is well documented, and the specific risks associated with chronic oral exposure to imatinib mesylate have been characterized as described in the Gleevec prescribing information (Gleevec product labeling). The most frequently reported adverse reactions with oral imatinib (greater than or equal to 20%) that were more frequent than placebo are diarrhea, fatigue, nausea, periorbital edema, reduction in hemoglobin, peripheral edema, rash and vomiting. Other known potential risks of imatinib reported in the Gleevec labeling, particularly for patients with comorbidities and risk factors, include edema and severe fluid retention, cytopenia, severe congestive heart failure and left ventricular dysfunction, severe hepatotoxicity, Grade 3/4 hemorrhage, gastrointestinal perforations, cardiogenic shock/left ventricular dysfunction, bullous dermatologic reactions, hypothyroidism, fetal harm when administered to a pregnant woman, growth retardation occurring in children and pre-adolescents, reports of motor vehicle accidents, and renal toxicity (Novartis Pharmaceuticals Corporation, 2022).

The safety profile of AV-101 is expected to be broadly consistent with that known for oral imatinib. However, inhaled AV-101 will be dosed at absolute levels lower than Gleevec and delivered directly to the lungs, reducing systemic exposure to imatinib. In published studies of oral imatinib mesylate, including 229 PAH patients who received imatinib 200 – 400 mg/day from 6 months to 204 weeks, similar AE profiles to those reported for Gleevec were observed. Subdural hematoma (SDH) occurred during imatinib treatment in 10 PAH patients in the published studies. Of the 10 patients, 1 died of SDH, 8 recovered, and 1 died of an unrelated cause. The exact relationship between oral imatinib mesylate treatment and SDH complications is unclear, but all patients who experienced SDH were on concomitant anticoagulation therapy. Imatinib is a competitive inhibitor of CYP3A4 and CYP2C9 enzymes that metabolize warfarin, which may result in increased plasma concentrations of these compounds and an increased risk of developing SDH. Anticoagulant use is disallowed in the AV-101-02 and AV-101-003 studies. Investigators are required to evaluate subjects for the presence of any signs or symptoms suggestive of intracranial bleeding such as: headache, confusion, vomiting, slurred speech etc.

In addition:

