6.8 Discontinuation of Study Drug and Subject Discontinuation/Withdrawal

6.8.1 Discontinuation of Study Drug

At the time of early study drug discontinuation subjects may elect to (1) discontinue from the study and agree to telephone contacts per the visit schedule, or (2) discontinue from the study, and withdraw consent to be contacted in the future for further collection of study-related data.

For subjects who withdraw from or are withdrawn from taking the study drug, every attempt should be made to follow the subject for long term outcomes. However, if a subject withdraws consent to be contacted, they must complete the Early Discontinuation (ED) Visit within 14 days of AV-101 discontinuation, and then the Safety Follow-Up visits as described in [Section 6.2.2](#) and [6.2.4](#).

For subjects who are lost to follow-up, or who died, Safety Follow-up Visits may not be possible. In any case, the appropriate eCRF section must be completed.

The subject must be discontinued from taking study drug in the event of any of the following:

Examples:

- Enrollment despite violation of an inclusion or exclusion criterion which, in the Investigator’s and/or Sponsor’s opinion, makes discontinuation of the subject necessary.
- Occurrence of an AE/SAE that makes discontinuation of study drug desired or considered necessary by the Investigator and/or the subject.
- Participation in any other interventional study during the duration of this study for which the Investigator considers discontinuation of the AV-101 necessary.
- Occurrence of pregnancy (for further details in case of pregnancy, refer to [Section 7.8](#)).
- If disease activity is considered unacceptably high and treatment escalation beyond permitted medication changes ([Section 5.9.1](#)) is warranted in the view of the Investigator.

- Anaphylaxis, anaphylactoid, or other severe or life-threatening hypersensitivity reactions, based on the Investigator judgement.
- Use of a nonpermitted medicine, as defined in [Section 5.9.2](#). This should first be confirmed with the CRO Medical Monitor before discontinuation of the study drug.
- Noncompliance, judged as significant by the Investigator or Sponsor including noncompliance to the required study considerations, as defined in [Section 5.8](#).
- Surgery considered by the Investigator or Sponsor to be major (see [Section 4.2](#)).

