Appendix 1 Abbreviations

Appendix 2 Sample Quality of Life Questionnaire

Appendix 3 Guidance for 6-Minute Walk Test

Appendix 4 Borg Dyspnea Index

Appendix 5 Management of Abnormal and Medically Important Laboratory Abnormality

Appendix 6 Investigator Signature Page

Appendix 1 Abbreviations

6MWD/6MWT	Six-minute Walk Distance/Test
ADE	Adverse Device Effect
ADL	Activities of Daily Living
AE	Adverse Event
AESI	Adverse Events of Special Interest
BDI	Borg Dyspnea Index
BID	Twice-daily dosing
BMI	Body Mass Index
BP	Blood Pressure
BSA	Body Surface Area
CFB	Change From Baseline
CI	Cardiac Index
CIOMS	Council for International Organizations of Medical Sciences
CO	Cardiac Output
CRF/eCRF	Case Report Form/Electronic Case Report Form
CRO	Contract Research Organization
CTCAE	Common Terminology Criteria for Adverse Events
DLCO	Diffusing Capacity of the Lungs for Carbon Monoxide
DOAC	Direct Oral Anticoagulant Therapy
DPI	Dry Powder Inhaler
DSD	Drug Safety Department
DSMB	Drug Safety Monitoring Board
ECG	Electrocardiogram
ECHO	Echocardiogram
eCRF	Electronic Case Report Form
ED	Early Discontinuation
EDC	Electronic Data Capture
emPHasis-10	Questionnaire for assessing Health-Related Quality of Life in pulmonary arterial hypertension
EOT	End-of-Treatment
FAS	Full Analysis Set

FC	Functional Class
FEV ₁	Forced Expiratory Volume in 1 second
FSH	Follicle Stimulating Hormone
FU	Follow-up
FVC	Forced Vital Capacity
GCP	Good Clinical Practice
GFR/eGFR	Glomerular Filtration Rate/estimated Glomerular Filtration Rate
HDPE	High Density Polyethylene
HEENT	Head, Ears, Eyes, Nose, Throat
HIPAA	Health Insurance Portability and Accountability Act
HIV	Human Immunodeficiency Virus
HR	Heart Rate
HRQoL	Health-Related Quality of Life
I/HPAH	Idiopathic/Heritable PAH
IB	Investigators' Brochure
ICF	Informed Consent Form
ICH	International Council for Harmonisation
IEC	Independent Review Committee
IFU	Instructions For Use
IMP	Investigational Medicinal Product
IRB	Institutional Review Board
IUD	Intrauterine Device
IUS	Intrauterine Hormone-Releasing System
IWRS	Interactive Web-Response System
LTE	Long-Term Extension
LVEDP	Left Ventricular End-Diastolic Pressure
LVEF	Left Ventricle Ejection Fraction
M	Meters
MAD	Multiple Ascending Dose
MMRM	Mixed Model for Repeated Measures
mPAP	Mean Pulmonary Arterial Pressure

mRAP	Mean Right Atrial Pressure
NOAEL	No-Observed-Adverse-Effect-Level
NHP	Non-Human Primates
NT-proBNP	N-Terminal Prohormone-B Natriuretic Peptide
OD	Optimal Dose
OR	Odds Ratio

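### Section 1.2.1 disallows anticoagulants without limit of class, but the Section 5.9.2 list that triggers stopping AV-101 names only vitamin K antagonists and DOACs, so the status of parenteral anticoagulants is contradictory

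*Combined protocol and SAP*

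**What the plan says.** Section 1.2.1 (Known Potential Risks) gives the SDH history: "Subdural hematoma (SDH) occurred during imatinib treatment in 10 PAH patients in the published studies". One of these patients died of SDH. The section calls the relationship to oral imatinib unclear, but adds that "all patients who experienced SDH were on concomitant anticoagulation therapy". It describes inhibition of the enzymes that metabolize warfarin as a possible mechanism, and then states: "Anticoagulant use is disallowed in the AV-101-02 and AV-101-003 studies".

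Section 5.9.2 (Prohibited Medicines) has two entries. One is inhaled prostacyclins. The other is "Warfarin (or any vitamin K antagonists), DOACs or dual antiplatelet therapy". Antiplatelet monotherapy is expressly allowed. The consequence is tied to that list: "Use of any of the above nonpermitted medicines and therapies require IMP discontinuation", with a cross-reference to Section 6.8.

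Appendix 1 expands DOAC as "Direct Oral Anticoagulant Therapy".

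Section 5.9.1 (Permitted Medicines) sets the default. Permitted medications are those the subject needs during the study "and which are not specifically prohibited by the protocol".

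Section 6.8.1 includes use of a nonpermitted medicine, as defined in Section 5.9.2, among the reasons for which study drug must be discontinued. It then adds: "This should first be confirmed with the CRO Medical Monitor before discontinuation of the study drug".

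**The concern.** The sentence in Section 1.2.1 follows directly on the SDH account and reads as the program's safeguard against that event. Its scope is all anticoagulants. The rule that would put it into effect covers two classes, both defined without reference to injected agents, and sits beside a default that admits whatever is not specifically prohibited. If a subject needs a parenteral anticoagulant, two careful readers of the same protocol can reach opposite conclusions about continuing AV-101.

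The first thing at stake is subject safety: a stated safeguard may not be applied. The second is interpretation of the safety data. SDH is an adverse event of special interest (Sections 6.5 and 7.1). With about 140 sites planned, concomitant anticoagulant exposure and discontinuation of AV-101 could vary with which section a site reads, while the protocol describes a study in which no such exposure is allowed.

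**Working it through.** No sample size, power or error rate is involved, so the check is a comparison of text by class of agent.

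| Class | Section 1.2.1 | Section 5.9.2 list and stopping trigger | Sections 5.9.1 and 5.9.2 read alone |
|---|---|---|---|
| Vitamin K antagonists | disallowed | listed, triggers stopping | not permitted |
| DOACs (oral, per Appendix 1) | disallowed | listed, triggers stopping | not permitted |
| Parenteral anticoagulants (e.g. heparins) | disallowed, since no class is exempted | not listed, no trigger | permitted if required |
| Dual antiplatelet therapy | not addressed | listed, triggers stopping | not permitted |

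The third row is the contradiction. Four steps lead to it:

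1. Section 1.2.1 places no limit on class, so it reaches injected agents.
2. Section 5.9.2 cannot reach them. Heparins are not vitamin K antagonists, and Appendix 1 confines DOAC to oral agents. Neither heparins nor any other parenteral anticoagulant is named in the readable text of the protocol.
3. The discontinuation rule applies to the medicines listed above it in Section 5.9.2, so an unlisted agent does not set it off. Section 6.8.1 does not widen the rule, because it defines nonpermitted medicines by reference to Section 5.9.2.
4. Section 5.9.1 excludes what the protocol specifically prohibits. It leaves open whether a general sentence in the risk section counts as a specific prohibition.

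The fourth row also matters. Because the list includes dual antiplatelet therapy, it is not confined to the warfarin interaction described in Section 1.2.1. That mechanism alone therefore does not explain where the list stops.

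On stopping, Section 5.9.2 states a consequence with no prior step, while Section 6.8.1 places Medical Monitor confirmation before discontinuation. Neither says whether dosing continues in the interval. Section 6 asks that immediate safety concerns be discussed with the Medical Monitor at once. It does not say that use of a prohibited medicine is such a concern, or what happens to dosing meanwhile.

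The one available figure is background. Section 1.2.1 gives 10 SDH cases and 229 PAH patients in published studies of oral imatinib. Assuming that all 10 are among the 229, 10 / 229 = 0.0437, or 4.4%. This is a crude proportion over exposures of 6 months to 204 weeks. It is not an estimate for inhaled dosing, for parenteral anticoagulants, or for a delay in stopping.

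**The case against.** The strongest reply is that Section 1.2.1 is itself protocol text and Section 5.9.1 refers to prohibition by the protocol as a whole, so the ban already covers parenteral agents. This stands against a stronger reading that a reader might take from Section 5.9, namely that heparins are permitted. The documents do not settle that; they contradict themselves. The reply does not remove the problem, because the list and its stopping trigger still omit these agents.

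The sponsor can also point to other protections. Signs of intracranial bleeding are assessed at telephone visits (Section 6.2.1) and study visits (Section 7.3), with further investigation if present (Section 6.5). Concomitant drugs are recorded by name, dose, duration and indication (Section 5.9.1). These points stand. Anticoagulant exposure could be identified when SDH events are reviewed, so unrecognized confounding should not be claimed. But detecting and recording events does not replace a consistent rule on exposure.

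Three further inferences are tempting and are not supported:

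- **That the benefit-risk judgement rests on the ban.** Section 1.2.3 cites lower doses delivered to the lung, Phase 1 tolerability, toxicology and a safety review committee. The Benefit-Risk Conclusion cites unmet need and monitoring. Neither mentions anticoagulants.
- **That an anticoagulated subject is eligible.** Section 4.2 has no anticoagulant criterion. However, Section 1.2.1 says the parent study disallows anticoagulants too, entry requires completing that study, and exclusion 1 leaves room for investigator judgement. Whether such a subject could reach Week 24 depends on the parent protocol, which is not among the documents.
- **That Sections 5.9.2 and 6.8.1 conflict on whether to stop.** They cross-refer and both require discontinuation. Only the place of the confirmation step and the dosing status meanwhile are unclear.

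**Conclusion.** The scope mismatch holds. The SDH safeguard stated in Section 1.2.1 is wider than the list and trigger in Section 5.9.2, and the status of parenteral anticoagulants is contradictory. Sites following Section 5.9 could give one with AV-101 against the stated safeguard. The unclear sequence between Sections 5.9.2 and 6.8.1 is a secondary point.

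The size cannot be stated. The documents give neither the share of the up to 462 subjects who would need a parenteral agent nor the class of anticoagulant used by the SDH patients. The 4.4% does not measure this gap. The conclusion rests on a literal reading of the sections and on the readable text; the Appendix 5 figure is not reproduced there. The text should be corrected because it bears on subject safety and the correction is cheap. It does not invalidate any planned analysis.

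**What to change.** Reconcile Sections 1.2.1, 5.9.1 and 5.9.2 so that the stated safeguard, the prohibited list and the discontinuation trigger have the same scope. This can be done in either of two ways:

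- make the Section 5.9.2 list match Section 1.2.1, addressing parenteral anticoagulants explicitly; or
- restate the safeguard in Section 1.2.1 so that it claims only what the list covers.

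In the same revision, make Sections 5.9.2 and 6.8.1 consistent on the Medical Monitor confirmation step and state the dosing status until confirmation is given. Which scope and which sequence are right is for the sponsor's clinicians to decide.

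The cost is protocol wording and a memo to sites. No new visits, procedures or data items are needed, since concomitant medication is already recorded.

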6.5.3 Resting Electrocardiogram (ECG)

Digital 12-lead ECGs for all subjects will be recorded at the site using an appropriate ECG machine.

- A standard, single, digital 12-lead ECG will be obtained as outlined in the Schedule of Assessments after the subject has been resting in the supine position for 5 minutes using an ECG machine that automatically calculates the heart rate and measures PR, RR, QRS, QT, and QTc intervals.

All digital ECGs will be documented by recording date and time of collection. All ECG results must be reviewed at the site by the Investigator or a medically qualified designee for clinical management of the subject. The Investigator will judge the overall interpretation as normal or abnormal. Clinical significance and the reason for the abnormality will be recorded in the source documents and in the eCRF. Abnormal values will not be recorded as AEs unless they are a clinically significant change and/or the reason for discontinuation of the study drug due to AEs or are SAEs.

If an ECG result reveals a QTc interval that exceeds 500 msec, or a QTc progression of ≥ 60 msec from baseline, the subject must follow the instructions for down titration of investigational product per [Section 5.5](#) (Also see [Section 5.9.2](#)).

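### The two-week QTc recheck in 5.9.2 is not the complement of its trigger: read literally, it leaves some subjects over the limits without an instruction and keeps others on drug

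*Combined protocol and SAP*

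**What the plan says.** Section 5.9.2 sets two triggers for dose reduction, the second with a limit of 60 msec or more: "an absolute prolongation of the QTc interval to a value > 500 msec, or develops a change from baseline in the QTc interval of". Sections 5.5 and 6.5.3 restate these triggers, make the reduction mandatory and refer to 5.9.2. Neither adds a recheck rule. The only reduction described is one step, from two capsules to one.

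After two weeks on the reduced dose the ECG is repeated, and two sentences govern what follows.

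- Keep, with two limbs joined by 'or', the second being a change under 60 msec: "If there is a shortening of the QTc interval to < 500 msec, or the change from baseline is". A subject who meets either limb continues at the lower dose.
- Stop: "If there is no change in the QTc interval after reducing the dose then the subject should be discontinued from study drug".

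Section 5.9.2 has one other QTc stop, for a subject who meets a trigger when the dose is already reduced: "If a subject has already undergone a dose reduction for other reasons, then they should discontinue study drug". It does not cover a subject whose reduction was itself for QTc.

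**The concern.** A recheck after a safety trigger should sort every subject into keep or stop, normally by asking whether the trigger is still met. Here the trigger is an 'or' of two limits, the keep rule is also an 'or', and the stop rule is a third criterion, an unchanged QTc. The logical complement of 'A or B' is 'not A and not B', so the keep rule is too wide and the stop rule too narrow.

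Because only one dose step exists, this visit is in effect the decision to continue or stop, and about 140 sites would make it. Table 1 marks ECGs at baseline, Week 4, Week 24 and early discontinuation or end of treatment, and none at the 12-weekly visits. A subject kept on drug after a Week 24 trigger therefore has no further scheduled ECG on treatment once the two-week recheck is done.

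**Working it through.** There is no sample size, power or error-rate figure to reproduce. The check is to code the rule as written and apply it.

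Inputs, all from 5.9.2, with b = baseline, q0 = QTc at the trigger and q1 = QTc at the recheck (msec):

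- Trigger: q0 > 500 or q0 − b ≥ 60.
- Keep: (q1 < q0 and q1 < 500) or q1 − b < 60.
- Stop: q1 = q0, which is 'no change' read literally.

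The QTc values below are illustrations; only the limits 500 and 60 come from the protocol.

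| b/q0/q1 | Change at recheck | Limit still breached | Keep met? | Stop met? | Instruction |
|---|---|---|---|---|---|
| 430/530/485 | 55 | none | yes | no | keep, as intended |
| 430/530/530 | 100 | both | no | yes | stop, as intended |
| 440/530/510 | 70 | both | no | no | none |
| 440/530/540 | 100 | both | no | no | none |
| 450/515/505 | 55 | QTc > 500 | yes (change limb) | no | keep |
| 430/510/495 | 65 | change ≥ 60 | yes (absolute limb) | no | keep |
| 400/470/465 | 65 | change ≥ 60 | yes (absolute limb) | no | keep |
| 480/510/510 | 30 | QTc > 500 | yes (change limb) | yes | both |

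In the row 400/470/465, QTc was never above 500. A fall of 5 msec satisfies the absolute limb, although the trigger was the change and the change is still 65.

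The 'already reduced' clause gives a comparison. A subject reduced earlier for another reason who shows QTc 495 with a change of 65 must stop. The subject 430/510/495, on the same reduced dose with the same reading, is told to stay. The second subject is improving, so this does not prove what was intended, but it shows the same reading leading to opposite actions.

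**Coverage.** Take b from 400 to 480 and q0 and q1 from b to 560, in 5-msec steps. Of 6,465 triggered combinations:

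- 2,652 are kept with no limit breached;
- 888 meet the keep rule while still over a limit, 28 of which also meet the stop rule;
- 221 meet the stop rule only;
- 2,704 have no instruction (978 with a shorter QTc, 1,726 with a longer one).

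These sum to 2,652 + 888 + 221 + 2,704 = 6,465. They count combinations on an assumed grid and say nothing about how many patients would be affected.

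**Alternative readings.** If 'no change' means that neither keep condition was reached, the 2,704 fall to zero, but the 'or' still keeps subjects over one limit. If instead every breached limit must be cleared before a subject is kept, the rows 450/515/505, 430/510/495 and 400/470/465 are no longer kept. With 'no change' still read literally, they then have no instruction. The rule works throughout only if both charitable readings are adopted together, and the text states neither.

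**The case against.** The strongest reply is contextual. The stop sentence follows directly on the keep sentence, so a clinician would take it as the other branch: the reduction did not work, so stop. Exact equality of two QTc readings is an implausible clinical criterion, and a site told to stop for an unchanged QTc would hardly continue when it is longer. This stands in part. A reader might infer that the gap exists on any interpretation, and it does not.

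Second, the 'or' may be deliberate, mirroring the trigger and keeping an improving subject on half the dose. The documents cannot exclude that, so the retention is not a proven drafting error. Intent would not, however, explain why an unchanged 480/510/510 is told both to stay and to stop.

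Third, a reader might infer that sites have no safeguard, or that the recheck is the only QTc stop rule. Neither is so. The stop for subjects already reduced exists. Section 6 says "Immediate safety concerns should be discussed with the CRO Medical Monitor immediately upon occurrence or awareness", with the decision to continue or stop as the purpose. Section 6.5.3 requires medically qualified review of every ECG. Section 6.8.1 states "The subject must be discontinued from taking study drug in the event of any of the following" and lists events and conditions that the investigator judges to require it. Section 7.7 handles Grade 3 and 4 events, though the documents do not settle whether a given QTc value counts as one. All these routes rest on judgement, so they soften the consequence without supplying a threshold.

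Finally, 5.9.2 attributes the QTc risk to high oral doses, and 1.2.1 reports no clinically important ECG changes in Phase 1. That argues for few affected subjects.

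**Conclusion.** The point holds as a defect of wording in a cardiac-safety rule. Read literally, the recheck gives no QTc-specific instruction to subjects still above both limits whose QTc has partly shortened or has lengthened. As worded, it also tells some subjects who still meet a trigger to stay, and it contradicts itself for an unchanged QTc above 500 with a change below 60. The first part assumes that 'no change' means an unchanged value. The second assumes that either keep limb is enough, which is what the sentence says.

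The number of subjects affected cannot be estimated from the documents and is probably small. No sample size, error rate or analysis result changes. The documents do not support the inference that subjects with worsening QTc would in practice be left on drug. They support only that the protocol does not say what to do. The clarification should be made because the first step is mandatory and the second, which decides whether drug continues, is not fully defined.

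**What to change.** **Minimum.** Replace the last sentence of the QTc paragraph in 5.9.2 with: *Otherwise study drug is discontinued.* This removes every no-instruction case and leaves the sponsor's retention rule as it is. On its own it would settle 480/510/510 in favour of staying on drug with QTc unchanged above 500, and it leaves the other subjects over one limit where they are.

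**Recommended.** Replace the last two sentences with: *If at the repeat ECG the QTc is ≤ 500 msec AND the change from baseline is < 60 msec, the subject remains on the reduced dose; otherwise study drug is discontinued.* These are the protocol's own limits, and they also settle a QTc of exactly 500, which is currently neither above nor below the limit. On the grid, each combination gets exactly one action: 2,652 keep and 3,813 stop.

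**Cost.** No procedure is added, and 5.5 and 6.5.3 need no change. The recommended version goes further than closing the gap: subjects who improve but stay over one limit, such as 430/510/495, would stop on one repeat tracing, since 6.5.3 specifies "A standard, single, digital 12-lead ECG will be obtained as outlined in the Schedule of Assessments". How many is unknown. The existing stop for subjects already reduced asks for no confirmatory ECG either. If the sponsor prefers to keep improving subjects, it should write that rule explicitly. Neither version covers a later re-trigger in a subject already reduced for QTc.
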